4.0 Introduction

This statistical analysis plan (SAP), describes the analysis to be completed for Levodopa-Carbidopa Intestinal Gel (LCIG, also known as Carbidopa/Levodopa Enteral Suspension [CLES] in the United States) Study S187.3.005 (Study 3005), dated 17 December 2013, which incorporates Global Amendments 1, 2, 3 and 4 and UK Amendments 2 and 3.01. It contains a technical elaboration of the principal features of the statistical analyses described in the protocol and is intended to guide the statistical programming work for the interim analysis to be conducted following the interim database lock completed in October 2015 as well as for the final analysis to be summarized in the Clinical Study Report (CSR).

A previous interim analysis was completed as described in SAP Version 2. For the previous interim analysis, all subject assessments completed on or before 04 May 2012 were included.

For the October 2015 interim analysis, all subject assessments completed on or before 30 September 2015 (the "Cutoff Date") will be included in the analysis.

All analysis data sets and statistical output will be produced by the Biostatistics department of Quintiles, Inc, Research Triangles Park, North Carolina, USA using the SAS[®] system Version 9.4 or higher.¹

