6.4 Day Numbers, Study Periods and Visit Windows: Related Definitions

6.4.1 General Definitions

Assessment days will be related to the date of the first infusion of 3005 study drug (First 3005 LCIG Infusion). Baseline is defined in Section [6.4.5](#) (Baseline Period). The Cutoff Date for the 2015 interim analysis will be 30 September 2015. Assessments and/or measurements performed after the Cutoff Date, adverse events or device complications with start dates after the Cutoff Date, and concomitant medications with start dates after

the Cutoff Date will not be included in the 2015 interim analysis. No cutoff date will be applied to the analysis for the final CSR.

The following reference dates will be defined for all subjects in the All Subjects Consented subject sample defined in Section 8.1.1.

- **Date of the First 3005 LCIG Infusion (Day 1, RFSTDTN):**

The actual dates of study drug administration are not recorded in the 3005 database. The dates when 3005 study drug is dispensed are recorded in the DA raw data panel. For analysis, the date of the first 3005 LCIG infusion will be defined as the first date that 3005 study drug was dispensed to the subject. The visit date recorded in the DM raw data panel will be used if the date the first study drug was dispensed is not available.

The date of the first 3005 LCIG infusion will be defined as Day 1 and is the key variable RFSTDTN and is used in the calculation of relative days.

- **Date of the Last 3005 LCIG Infusion (RFENDTN):**

For subjects who have prematurely discontinued or completed the study, the date of the last 3005 LCIG infusion will be the earliest of 1) the date of last study drug administration collected on the DS raw data panel, 2) the date of discontinuation or study completion collected on the DS raw data panel and 3) the Cutoff Date (interim analysis only).

For the 2015 interim analysis, the date of the last 3005 LCIG infusion for all ongoing subjects will be the Cutoff Date.

- **Duration of 3005 LCIG Infusion (LDA):**

The Duration of 3005 LCIG Infusion or exposure to treatment is equal to the day number of the Last 3005 LCIG Infusion (LDA) and is derived as follows from the previous two dates:

$$\text{LDA (days)} = (\text{Date of the Last 3005 LCIG Infusion [RFENDTN]} - \text{Date of the First 3005 LCIG Infusion [RFSTDTN]}) + 1$$

LDA then indicates the relative day of the last 3005 LCIG infusion for each subject.

- **Date of Last 3005 PEG-J Exposure (RFENDT2N):**

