LCIG is administered as part of a therapeutic system that includes devices and implantation procedures. Subjects who discontinue LCIG therapy are to have their PEG-J removed.

For subjects who have prematurely discontinued or completed the study, and have reported a final PEG-J removal on the DI raw data panel that is after their last day of study drug administration and before the Cutoff Date (interim analysis only), their date of last 3005 PEG-J exposure will be the date of PEG-J removal. For all other subjects who have prematurely discontinued or completed the study, their date of last 3005 PEG-J exposure will be the earlier of 1) the date of discontinuation or study completion collected on the DS raw data panel, and 2) the Cutoff Date (interim analysis only).

For the 2015 interim analysis, the date of the last 3005 PEG-J exposure for all ongoing subjects will be the Cutoff Date.

The date of the last 3005 PEG-J exposure is the key variable RFENDT2N.

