The percentage of each of the aforementioned AE types will be determined as the number of subjects with at least one mention of the AE type relative to the number of subjects at risk. A subject will be considered at risk if the subject is in the Safety subject sample.

In addition to the aforementioned AE types, AEs reported by the Investigator as related to device complications will also be summarized. Device complications are captured in the DE raw data panel and associated AEs are captured in the AE raw data panel.

Investigators link the AEs that are related to device complications by entering an AE number in the DE raw data panel.

The incidence and prevalence of TEAEs during each 3005 Treatment Year will be summarized using the study day intervals described in Section 6.4.9. AE start days and Treatment Period end days will be calculated relative to the start of 3005 LCIG infusion (RFSTDTN) as follows:

$$\text{AE Start Day} = (\text{AE Start Date} - \text{Date of First 3005 LCIG Infusion}) + 1$$

$$\text{Treatment Period End Day} = ([\text{Date of Last 3005 PEG-J Exposure} + 30 \text{ Days}] - \text{First Date of 3005 LCIG Infusion}) + 1$$

For summaries of incidence, the count (and numerator for percentage calculations) will be the number of subjects who had their first treatment-emergent occurrence of the PT start

within the study day range for the 3005 Treatment Year. Each subject will be counted at most once within each SOC and PT.

For summaries of prevalence, the count (and numerator for percentage calculations) will be the number of subjects who had a treatment-emergent occurrence of the PT start within the study day range for the 3005 Treatment Year or who had an earlier treatment-emergent occurrence of the PT that had not ended prior to the start of the study day range for the 3005 Treatment Year.

The denominator for both incidence and prevalence percentage calculations will include all subjects whose Treatment Period End Day is within or greater than the study day range for the 3005 Treatment Year.

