9.1 Subject Disposition

Subject disposition (DS) will be summarized for all centers/countries combined by means of the default summary statistics described in Section 6.0 (General Definitions, Methods, Naming Conventions and Data Handling).

Subject Samples:	Tables	All subjects consented and Efficacy Sample US Subset
	Listings	All subjects consented
	Figures	Not applicable
Subgroups:		Not applicable
Abbreviation:		DS

Standard Presentations

- DST001 The primary reason for premature discontinuation after consent, as recorded on the "Study Termination" form, will be presented. The primary reason for premature discontinuation includes:
- Adverse Event
 - Lack of Efficacy
 - Lost to Follow-up
 - Withdrew Consent
 - Administrative
 - Protocol Violation

The number of subjects who have completed the study and the number whose participation in the study is ongoing will also be presented. The percentage of subjects will be calculated relative to the number of consenting subjects.

- DST002 Subject validity/subject sample status will be summarized with the reason for exclusion from the Safety sample. The only reason for exclusion from the safety sample will be that the subject did not infuse any study medication after providing informed consent.
- DST003 The number and percentage of subjects prematurely discontinuing in each 3005 treatment year will be summarized.

Standard subject data listings include:

- DSL001 A listing of subjects who prematurely discontinued their participation in the study prior to receiving 3005 LCIG.

DSL002 A listing of subjects who discontinued participation after receiving 3005 LCIG will be presented. The relative treatment day of last contact with the subject and the last day of 3005 LCIG infusion, as captured on the "Study Termination" CRF form will be calculated as:

- Relative Treatment Day of Last Contact = (Date of Last Contact – Date of First 3005 LCIG Infusion) + 1
- Relative Treatment Day of Last 3005 LCIG Infusion = (Date of Last 3005 LCIG Infusion – Date of First 3005 LCIG Infusion) + 1

DSL003 Exclusion from the Safety subject sample together with the reason(s) for exclusion will be presented. This listing will include all possible reasons for exclusion per subject.

Study Specific Presentations

Not applicable.

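### At the 2015 interim, the by-year adverse-event and device denominators run 30 days past the Cutoff Date, and disposition status has no stated as-of date (minor)

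*SAP*

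**What the plan says.** **Cutoff.** SAP 6.4.1 states: "The Cutoff Date for the 2015 interim analysis will be 30 September 2015". It leaves out later assessments, "adverse events or device complications with start dates after the Cutoff Date, and concomitant medications with start dates after" that date. Disposition records and tube placements are not named in the list. The same section says that no cutoff applies to the final report. SAP 4.0 gives the general rule that "For the October 2015 interim analysis, all subject assessments completed on or before 30 September 2015" are in, and refers to the "interim database lock completed in October 2015".

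**Exposure dates.** SAP 6.4.1: "For the 2015 interim analysis, the date of the last 3005 PEG-J exposure for all ongoing subjects will be the Cutoff Date". For subjects recorded as discontinued or completed, the derived last-infusion and last PEG-J dates are also limited by the Cutoff.

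**By-year denominators.** SAP 8.5.1 defines Treatment Period End Day as (last PEG-J exposure + 30 days) minus first infusion, plus 1. The denominator for both incidence and prevalence "will include all subjects whose Treatment Period End Day is within or greater than the study day range" of the year in question. SAP 8.5.5.1 (device complications) and 8.5.5.2 (tube replacements) use the same end day. SAP 6.4.6 sets the 30-day adverse-event gap with no interim exception.

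**Disposition.** SAP 9.1 builds DST001 from the Study Termination form and adds: "The number of subjects who have completed the study and the number whose participation in the study is ongoing will also be presented". It gives no as-of date.

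**The concern.** The Cutoff removes events from the numerator, but the denominator window runs on for another 30 days. For a subject who stopped well before the Cutoff, those 30 days are real follow-up and the rule is right. For an ongoing subject they are days on which nothing can be counted. Such a subject cannot contribute a new onset, so AET011, DCT003 and DCT006 are diluted, most in the sparse late years that carry the long-term safety information. In AET014 an unresolved earlier event puts the same subject in the numerator as well, so prevalence can rise or fall. DIT002 shares the end day, but tube placements after the Cutoff are not on the exclusion list, so the direction there is not settled.

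Two other by-year rules in the SAP do not behave this way. The concomitant-medication denominator (8.2.4) requires the last infusion day to fall within or after the year. EXT001 (9.8) requires at least one day of exposure in it. The same ongoing subject can therefore appear in a late-year adverse-event column and be absent from that year in the medication and exposure tables.

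Disposition raises a separate question of consistency. The caps on the derived dates are needed only if terminations after the Cutoff can be in the interim data, yet nothing says how such a subject is classified.

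**Working it through.** The plan gives no interim denominators, event rates or entry dates, so there is no figure of its own to reproduce. The date rules can be applied directly.

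**One subject.** First infusion 17 October 2011, ongoing at the Cutoff.
- Day at Cutoff = (30 September 2015 − 17 October 2011) + 1 = 1444 + 1 = 1445.
- Treatment Period End Day = 1445 + 30 = 1475.
- Year 5 is Days 1461 to 1825 (SAP Table 3). Since 1475 ≥ 1461, the subject enters the Year 5 denominator.
- No event after Day 1445 is admitted, so observable Year 5 time is zero.

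The same holds for any subject whose last PEG-J exposure is the Cutoff and whose day number then is 1 to 30 below the start of a year. For Year 5 these are Days 1431 to 1460, which means first infusion from 2 to 31 October 2011.

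**Size.** Let *s* be the first day of a Treatment Year. Assume day numbers at the Cutoff are uniform from *lo* to *hi*, with *lo* ≤ *s* − 30. Then

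inflation = (number with day + 30 ≥ *s*) / (number with day ≥ *s*) − 1 = 30 / (*hi* − *s* + 1).

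| Assumed days | Year 3 (*s* = 731) | Year 4 (1096) | Year 5 (1461) | > Year 5 (1826) |
|---|---|---|---|---|
| 365–2520 | 30/1790 = 1.7% | 30/1425 = 2.1% | 30/1060 = 2.8% | 30/695 = 4.3% |
| 365–2100 | 30/1370 = 2.2% | 30/1005 = 3.0% | 30/640 = 4.7% | 30/275 = 10.9% |
| 600–2000 | 30/1270 = 2.4% | 30/905 = 3.3% | 30/540 = 5.6% | 30/175 = 17.1% |

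Only the upper end of the first row (2520) matches a figure in the SAP, the Month 84 target day in Table 2. As an illustration, a true onset percentage of 20% beyond Year 5 would print as 20/1.043 = 19.2%, 20/1.109 = 18.0% or 20/1.171 = 17.1%.

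An extreme case is a spread of 730–1825. Year 5 is then inflated by 30/365 = 8.2%, and the > Year 5 column holds only subjects with no observed time. The Month 84 window suggests that the SAP does not expect this.

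**Subjects who have already left.** Those who reached a year before leaving belong in its denominator too.
- If the uniform spread describes subjects still ongoing, and departures run at an assumed rate *r* per year, the denominator is proportional to (e^(*r*(*hi* − *s* + 1)/365) − 1)/(e^(*r*/365) − 1). With *r* = 0.4 and *hi* = 2100, Year 3 inflation falls from 2.2% to 30/3181 = 0.9%, and > Year 5 from 10.9% to 30/320.8 = 9.4%.
- If the spread instead describes everyone who entered, attrition scales both counts alike. A simulation with 275 entrants on 365–2520 and 5% to 20% attrition per year left the percentages almost unchanged (> Year 5 stayed at 4.3%).

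**Disposition.** Expected departures between Cutoff and lock = *N* × (1 − e^(−rate × days/365)), assuming 100 to 200 ongoing subjects and 0.1 to 0.4 departures per subject-year.
- Lock on 31 October (31 days): 100 × (1 − e^(−0.0085)) = 0.8, up to 200 × (1 − e^(−0.0340)) = 6.7.
- Lock on 5 October (5 days): about 0.1 to 1.1.

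Such a subject could be shown as discontinued or completed in DST001 while derived exposure ends at the Cutoff. If the event that ended participation began after the Cutoff, it would be missing from AET005.

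**The case against.** The strongest reply is about scale. One descriptive, single-arm interim is affected, no alpha is tested (Protocol 13.4), and no decision rule is attached to it. Overall adverse-event percentages use the whole sample (SAP 9.11.1) and do not change. The by-year percentages are crude by design: one day in a year counts as a full subject. Under the uniform assumption, about 365 days' worth of ongoing subjects are part-way through a complete year, against 30 days' worth of spurious entrants. All of this stands and limits the severity. It does not excuse admitting subjects who have no observable time at all.

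A reader might infer that disposition is not cut at the interim at all and that its tables will contradict the others. The text does not support that. The derived last-infusion and PEG-J dates are capped at the Cutoff. DST003 allocates discontinuations by last dose date (SAP 8.1.5), so it is capped too if the derived date is used. SAP 4.0 limits the interim to assessments up to the Cutoff, and completion requires a final visit (8.1.5), so a later final visit may already be excluded. What remains is that no rule is stated for status. The tables can disagree, but only if a departure was recorded between the Cutoff and the October lock.

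**Conclusion.** The denominator point holds on the text: events stop at the Cutoff, the end day runs 30 days beyond it for ongoing subjects, and nothing caps it. By-year onset percentages in AET011, DCT003 and DCT006 are understated at the interim. AET014 can move either way, and the effect on DIT002 is unclear. Under the three assumed uniform spreads, denominators are inflated by 1.7% to 5.6% for Years 3 to 5 and by 4.3% to 17.1% beyond Year 5. The figures are lower where subjects who left after reaching the year form a large share. The actual size depends on entry dates that the documents do not give.

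The disposition point is a gap in specification that affects a few subjects at most, and almost none if the lock came early in October.

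It would go too far to conclude that the study's long-term risk estimates as a whole are biased down: only by-year interim tables are touched, and the final report has no cutoff. Severity: minor.

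**What to change.** For the interim only:

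- In SAP 8.5.1, 8.5.5.1 and 8.5.5.2, set Treatment Period End Day to the day number of the earlier of (last PEG-J exposure + 30 days) and the Cutoff Date. All three sections need the change; amending 8.5.1 alone would leave the device and tube denominators as they are. The cap also handles subjects who stopped less than 30 days before the Cutoff.
- In SAP 6.4.1, state that disposition status and reason, and tube placements and removals, are taken as of the Cutoff Date. A discontinuation or completion dated after 30 September 2015 is then shown as ongoing.

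The final analysis stays as planned. The cost is a few sentences and minor programming, and late-year onset percentages will come out slightly higher. The cap does not address the dilution from subjects who are part-way through a year, which is a feature of the by-year definition.

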6.4.2 Initial Screening Period

Height and background information related to medical and neurological history and PD diagnosis was only collected during the Screening Period of the first LCIG study that a subject participated in. For example, subjects who entered the 3005 study after completing the 3003 open-label study would have completed one of the two Phase 3, double-blind studies, Study 3001 or 3002, before their enrollment in Study 3003. For these subjects, certain background information, e.g., medical history, neurological history and PD diagnosis information, was only collected prior to Study 3001 or 3002. This information will be retrieved from the relevant study databases and summarized for the subjects enrolled in Study 3005.

6.4.3 Initial PEG-J Placement

Subjects enrolled in Study 3005 had their initial PEG-J placement in Study 3001, 3002 or 3004. To allow the overall duration of PEG-J exposure to be summarized for each subject

in Study 3005, the date of initial PEG-J placement will be retrieved from the relevant study database.

6.4.4 Initial LCIG Infusion

Subjects enrolled in Study 3005 had their first LCIG infusion in the same study as their initial PEG-J placement (Studies 3001, 3002 or 3004) except for subjects who received levodopa-carbidopa capsules and placebo gel in Study 3001 or Study 3002. These subjects had their first LCIG infusion in Study 3003. To allow the overall duration of LCIG exposure to be summarized for each subject in Study 3005, the date of initial LCIG infusion will be retrieved from the relevant study database.

For US subjects who completed Daily Dosing Diaries in Study 3005 following Amendment 4, the total daily levodopa dose at the end of the subject's initial LCIG titration period will be retrieved from the relevant database to allow the change in dose from initial titration to final Study 3005 visit to be determined.

To provide context for changes in efficacy measures observed during Study 3005, the respective change observed between initial LCIG infusion and Study 3005 final visit will be determined and summarized. For subjects who completed efficacy assessments in Study 3005, their baseline value from the study in which they had their first LCIG infusion will be retrieved from the relevant database and considered their value at initial LCIG infusion.

6.4.5 Baseline Period for Study 3005

The Baseline Period for Study 3005 is defined as the time before the first 3005 LCIG infusion. For efficacy measures, the final value in the previous study (Study 3003 or Study 3004) will be retrieved from the relevant database and will be considered the 3005 baseline value. For safety evaluations, the final assessment in the previous open-label LCIG study or in 3005 that is on or before the date of the first 3005 LCIG infusion will be used as the 3005 Baseline value. For systolic blood pressure, diastolic blood pressure and

pulse, the final assessment where results are present for both the supine and standing position will be considered baseline.

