11.1.6 Vital Signs

Orthostatic vital signs including pulse, blood pressure, and body temperature will be measured at the times indicated in [Table 2](#). Temperature measurements should be assessed by a consistent method (e.g. all oral or all ear [tympanic membrane] measurements) and by the same method as baseline, if baseline is available. Weight will be measured at the times indicated in [Table 2](#).

Systolic blood pressure (SBP), diastolic blood pressure (DBP) and pulse rate are to be measured while the subject is supine (after 3 to 5 minutes) and standing (after 2 minutes).

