Subject disposition will be summarized including the primary reason for premature discontinuations and a listing of all subjects not included in the safety population.

Descriptive statistics will be provided for demographics and baseline characteristics.

Concomitant medication use will be summarized over time.

Baseline and Endpoint

Unless noted otherwise, the baseline value for a variable is defined as the last non-missing value collected in the current study or the previous open-label LCIG study before the first dose of study drug in the current study.

The endpoint value for a variable is defined as the last non-missing value assigned to the treatment period in the current study for the subject. For subjects transferring to commercial product, the end of treatment in the current study will be the last dose of study drug. For subjects who are discontinuing LCIG treatment, the end of treatment in the current study will be the removal of the PEG-J tube.

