8.5.3 Vital Signs and Weight

The measured vital signs include:

- Weight (kg).
- Body Temperature (degrees Celsius) and Route of Measurement.
- Systolic Blood Pressure (SBP [mmHg]), supine and standing.
- Diastolic Blood Pressure (DBP [mmHg]), supine and standing.
- Pulse Rate (bpm), supine and standing.

The following orthostatic vital signs will be calculated based on measurements in the supine and standing positions:

- Orthostatic SBP (mmHg) = Standing SBP – Supine SBP
- Orthostatic DBP (mmHg) = Standing DBP – Supine SBP
- Orthostatic Pulse Rate (bpm) = Standing Pulse Rate – Supine Pulse Rate

See Section 8.2.2 (Other Baseline Characteristics) for the derivations and conversions of the aforementioned variables. At each scheduled visit, preferably by the same observer, supine and standing SBP, DBP, and pulse rate will be measured using the same arm after the subject has been in the position for 2 minutes.

Potentially clinically significant (PCS) vital signs values will be identified. A vital sign value will be considered potentially clinically significant if it satisfies the criteria presented in Table 5 and is also more extreme than the subject's corresponding baseline value.

Table 5. Criteria for Identification of Potentially Clinically Significant (PCS) Vital Sign and Weight Values

Variable	Unit	Very Low (VL)	Very High (VH)
SBP ^a	mmHg	Value ≤ 90 and > 30 decrease from Baseline	Value ≥ 180 and > 40 increase from Baseline
DBP ^a	mmHg	Value ≤ 50 and > 30 decrease from Baseline	Value ≥ 105 and > 30 increase from Baseline
Pulse Rate ^a	bpm	Value ≤ 50 and > 30 decrease from Baseline	Value ≥ 120 and > 30 increase from Baseline
Temperature	°C	NA	Value ≥ 38.3 and ≥ 1.1 increase from Baseline
Orthostatic SBP (Hypotension)	mmHg	Decrease of ≥ 30 in SBP (supine to standing)	NA
Orthostatic DBP (Hypotension)	mmHg	Decrease of ≥ 20 in DBP (supine to standing)	NA
Weight	kg	Decrease of ≥ 7% from Baseline	Increase of ≥ 7% from Baseline

a. Both for supine and standing.

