9.11.3 Vital Signs

Subject Samples:	Tables	Safety sample
	Listings	All subjects consented
	Figures	Not applicable
Subgroups:		Not applicable
Abbreviation:		VS

Standard Presentations

- VST001 Summary of quantitative vital signs assessments will be presented, for all centers/countries combined, using default summary statistics. At each assessed visit, summary statistics will be presented as well as for the change from Baseline at each post-baseline visit.
- VST002 For each variable with a PCS criterion (as presented in [Table 5](#)), the incidence of PCS values will be presented. The percentage per parameter is defined as the ratio of the number of subjects with at least one PCS value occurring at a post baseline visit that is more extreme than their baseline value and the total number of subjects in the subject sample with a post baseline measurement of the specified parameter.

In addition, all vital signs data will be presented as follows:

- VSL001 A listing of PCS values together with standard demographic data will be presented by-subject and within-subject by PCS vital signs test criterion by visit.
- VSL002 Vital signs data will be presented by-subject and within-subject by vital signs test and visit.

Study Specific Presentations

- VST003 For each variable with a PCS criterion (as presented in [Table 5](#)), the incidence of PCS values will be presented by visit. For a specific visit, the percentage per parameter is defined as the ratio of the number of subjects with at least one PCS value occurring at a specific post-baseline visit that is more extreme than their baseline value and the total number of subjects in the subject sample with a post baseline measurement of the specified parameter for the visit.

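### The SAP takes blood pressure and pulse baselines only from paired supine and standing readings, and keeps subjects without a baseline in the denominators of the abnormal vital-sign tables

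*SAP*

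**What the plan says.** SAP 6.4.5 gives a general safety baseline: "the final assessment in the previous open-label LCIG study or in 3005 that is on or before the date of the first 3005 LCIG infusion". It then narrows this for systolic pressure, diastolic pressure and pulse, where "the final assessment where results are present for both the supine and standing position will be considered baseline". No fallback is given for a subject with no paired assessment.

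Protocol 13.3 has no such condition. Its default rule, which leaves room for stated exceptions, reads: "the baseline value for a variable is defined as the last non-missing value collected in the current study or the previous open-label LCIG study". Only values that precede dosing in this study qualify.

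The PCS rules in SAP 8.5.3, Table 5, depend on that baseline. Low systolic pressure is "Value ≤ 90 and > 30 decrease from Baseline" and low diastolic pressure is "Value ≤ 50 and > 30 decrease from Baseline", each applied to supine and to standing values. In addition, any PCS value must be one that "is also more extreme than the subject's corresponding baseline value".

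The VST002 denominator in SAP 9.11.3 is "the total number of subjects in the subject sample with a post baseline measurement of the specified parameter". VST003 uses the same definition visit by visit. Neither requires a baseline.

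**The concern.** Supine and standing pressures are separate variables with their own summary tables. A supine reading is valid whether or not a standing reading was taken with it, so discarding it because its partner is missing loses usable data. Two consequences follow.

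- **Outdated baseline.** If the last assessment before Day 1 has one position only, an older paired assessment becomes the baseline. PCS status and the VST001 changes are then measured from a value that does not describe the subject at entry to this study.
- **No baseline.** If no paired assessment exists, no change can be computed. The subject cannot be a case but is still counted in the percentage, and so appears as a non-event.

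The rule is also one-sided: SAP 6.4.8 tests every reported post-baseline vital sign against the PCS criteria, with no pairing condition. Long-term safety is the primary statistical objective (protocol 13.1), so these tables are part of the main output.

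**Working it through.** The documents state no figure on this point: no count of unpaired assessments, no blood pressure SD and no PCS rate. There is nothing to reproduce. The check traces the rule through the tables and then sizes it on assumed inputs.

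**Step 1. Which variables the choice of baseline rule affects**

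| Variable | Needs both positions? | SAP 6.4.5 baseline | Last non-missing value |
|---|---|---|---|
| Supine or standing SBP, DBP, pulse | No | Last paired assessment | Last reading in that position |
| Orthostatic SBP, DBP, pulse | Yes | Last paired assessment | Last paired assessment |

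Table 5's two rows labelled hypotension are drops from supine to standing within one visit. Baseline enters them only through the more-extreme clause, and an orthostatic baseline cannot be formed without a pair under either rule. The effect of the baseline rule on those numerators is zero.

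**Step 2. When an older baseline changes PCS status**

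A systolic value of 90 in this study is PCS low only if baseline exceeds 90 + 30 = 120. A diastolic value of 50 is PCS low only if baseline exceeds 50 + 30 = 80. Status changes whenever the older paired reading and the later single reading lie on opposite sides of that line. An older reading that is higher adds a case; one that is lower removes a case.

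**Step 3. Subjects with no baseline**

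Let f be the share of the denominator without a baseline and p the PCS percentage among those with one. The displayed percentage is (1 − f) × p. With p assumed to be 5%:

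- f = 2%: 0.98 × 5% = 4.90%
- f = 5%: 0.95 × 5% = 4.75%
- f = 10%: 0.90 × 5% = 4.50%

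The relative understatement equals f. Of the planned 275 subjects, these shares are 5.5, 13.75 and 27.5 (about 6, 14 and 28). The same formula applies to any row that needs a baseline. That includes weight and temperature, whose Table 5 rules also use change from baseline, and the orthostatic rows through the more-extreme clause.

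**Step 4. Size for low supine systolic pressure, both parts of the rule applied**

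All inputs are assumed: mean 115 to 125 mmHg, SD 15 to 20 and between-visit correlation 0.6.

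- *Per assessment.* The last reading gives a PCS-low rate of 0.13% to 1.7%. An older baseline with no drift gives 0.13% to 3.3%, where its correlation with the later value is 0.6 down to 0.4. With 5% of subjects affected, the overall rate moves by 0.00 to +0.08 points with an older baseline, and by −0.01 to −0.09 points with none.
- *Per subject.* VST002 counts a subject once for any PCS value at any visit, so this is the relevant scale. The simulation used 4 to 8 visits and an older baseline 10 to 20 mmHg higher. An affected subject's chance of being flagged is then multiplied by a factor between about 1.8 and 5 (up to 6.5 in a wider set of inputs). With 5% affected, the table moves by +0.04 to +0.85 points. If the older baseline is instead 10 to 20 mmHg lower, it moves by −0.02 to −0.44 points. With no baseline it moves by −0.02 to about −0.50 points.

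Taking the change condition alone would overstate the effect. With within-subject SD s and downward drift d, P(fall > 30) = 1 − Φ((30 − d)/(s√2)). For s = 12 to 15 this is 4% to 8% at d = 0 and 12% to 32% at d = 10 to 20. It leaves out the condition that the value be 90 or below.

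**The case against.** - **Taking all three baselines from one assessment is defensible.** It keeps supine, standing and orthostatic values consistent on the same date. This stands: the per-position rule gives that up in a few subjects, and choosing between the two is partly preference.
- **It is not a flat contradiction of the protocol.** Protocol 13.3 allows exceptions, and protocol 13.0 leaves analysis details to the SAP. This stands in part. SAP 10.1 does declare the changed efficacy baseline, so this departure belongs there too.
- **Few subjects should be affected.** Protocol 11.1.6 has both positions measured, and the look-back reaches into the preceding open-label study, planned at 12 months (SAP 5.2). This stands for frequency. It does not remove the need for a rule: SAP 6.5 refers missing-data handling to Section 8, and SAP 8.5.3 says nothing about a missing baseline. For temperature, protocol 11.1.6 itself allows that a baseline may not be available.
- **The denominator problem is separate.** It would exist for weight and temperature without any pairing rule. That is true, and is why the correction should cover every criterion that needs a baseline. The pairing rule adds blood pressure and pulse subjects to it.
- **Individual values remain visible in listing VSL002.** They do, but the summary percentages would still be wrong.

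A reader might infer that missing standing values cluster in subjects too disabled or too orthostatic to stand, so that the loss is selective. That is plausible, but neither document says that standing values are missing, why, or in whom.

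**Conclusion.** The point holds as a defect in the baseline and denominator rules, probably small in effect. SAP 6.4.5 passes over valid single-position readings without need and gives no fallback. Supine and standing PCS counts and VST001 changes can shift in either direction. A missing baseline can only lower the VST002 and VST003 percentages, by a relative amount equal to the share of subjects without one if their risk is the same as the others'.

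A reader might go further and conclude that hypotension is miscounted. The documents do not support that. The Table 5 criteria labelled hypotension are the orthostatic ones, and their numerators are the same under either baseline rule; only their denominators are touched, by subjects with no paired baseline. The protocol 10.8 warning about postural hypotension therefore does not show harm from this rule.

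The sizes given, less than 1 percentage point with 5% of subjects affected, rest entirely on assumed shares, blood pressure distributions and drift. They show scale and are not estimates for this trial.

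**What to change.** 1. In SAP 9.11.3 (VST002 and VST003), for every criterion that needs a baseline, including weight and temperature, limit the denominator to subjects with both a baseline and a post-baseline value. In VST003, the post-baseline value is the one at that visit.
2. In SAP 6.4.5, for supine and for standing systolic pressure, diastolic pressure and pulse, use the last non-missing value in that position on or before Day 1. Require both positions at the same assessment only for the orthostatic variables.
3. If the paired rule is kept instead, list it in SAP 10.1 and fall back to the last single-position value when no paired assessment exists.

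The cost is a few SAP sentences and a small programming change, using data already collected. The downside of item 2 is that supine, standing and orthostatic baselines may carry different dates in a few subjects. Item 1 gives the correct percentage among evaluable subjects; it does not recover events in subjects without a baseline, which is a reason to adopt item 2 or the fallback as well.
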